### **10.4.2. Shifts in CTCAE Toxicity Grade**

Shifts in Common Terminology Criteria for Adverse Events (CTCAE) toxicity grade of laboratory tests from baseline to worst value (scheduled or unscheduled), last value (scheduled or unscheduled), and at each scheduled post-baseline visit will be provided by treatment group. The toxicity grades are in the CTCAE version 4.03.

Summaries will present the number and percentage of patients with shifts in laboratory toxicity grade by treatment group.

### **10.4.3. Incidence of Liver Function Abnormalities**

The incidence of patients with abnormalities in liver function tests (ALT, AST, alkaline phosphatase [ALP], and total bilirubin) will be summarized overall for the following categories:

- ALT and AST:
  - $>1 \times \text{ULN}$
  - $>2 \times \text{ULN}$
  - $>3 \times \text{ULN}$
  - $>5 \times \text{ULN}$
  - $>8 \times \text{ULN}$
- ALP:
  - $>1 \times \text{ULN}$
  - $>1.5 \times \text{ULN}$
  - $>2.5 \times \text{ULN}$
  - $>5 \times \text{ULN}$

- Total bilirubin:
  - $>1 \times \text{ULN}$
  - $>1.5 \times \text{ULN}$
  - $>2 \times \text{ULN}$
  - $>3 \times \text{ULN}$

Scatterplots of ALT vs AST, ALT vs total bilirubin, and AST vs total bilirubin maximum post-baseline values will be presented. If appropriate, evaluation of drug-induced serious hepatotoxicity plots of ALT or AST  $>3 \times \text{ULN}$  accompanied with total bilirubin by treatment group will be presented for assessment of potential drug induced liver injury. A listing of patients with  $>2 \times \text{ULN}$  total and  $>3 \times \text{ULN}$  ALT or AST at any time on study will be provided.

#### 10.4.4. Incidence of Clinically Significant Local Laboratory Assessments

The incidence of patients with clinically significant local labs will be summarized by treatment group and overall at each baseline and post-baseline visit for each local laboratory parameter collected. Percentage will be based on the number of patients with local laboratory results for each parameter and visit.

### 10.5. Vital Signs

The results and change from baseline to each post-baseline scheduled visits will be summarized for blood pressure (systolic and diastolic), heart rate, respiration rate, temperature, and weight.

The number and percentage of patients meeting the following criteria at any time during the study will also be summarized:

- Systolic blood pressure:
  - $\leq 100$  mmHg
  - A decrease from baseline more than 30 mmHg
  - $>180$  mmHg
  - An increase from baseline more than 40 mmHg
- Diastolic blood pressure:
  - $\leq 60$  mmHg
  - A decrease from baseline more than 20 mmHg
  - $>105$  mmHg
  - An increase from baseline more than 20 mmHg
- Heart rate:
  - $<45$  beats per minute
  - A decrease from baseline more than 20 beats per minute
  - $>120$  beats per minute
  - An increase from baseline more than 20 beats per minute

For the analysis of orthostatic hypotension, the number and percentage of patients with >20 mmHg decrease in systolic blood pressure at any time and the number and percentage of patients with > 10 mmHg decrease in diastolic blood pressure at any time will be presented.

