## 9.6. Vital Signs

Vital signs, including blood pressure, heart rate, temperature, respiration rate, weight, and height, will be performed according to the Schedules of Study Events in [Section 15.1](#). Height will only be recorded at screening of the double-blind period. Vital signs should be measured prior to phlebotomies for clinical laboratory evaluations.

Blood pressure will be measured after the patient has been sitting comfortably in a chair for at least 5 minutes prior to obtaining 3 readings, using the same arm for each reading; the mean of the last 2 readings will be recorded. In addition to these blood pressure measurements, measurements of blood pressure intended to detect possible orthostatic hypotension will be performed at each visit according to US Centers for Disease Control and Prevention guidelines ([US CDC 2017](#)). Heart rates will be measured with each positional blood pressure reading for orthostatic hypotension detection. This should be done after the sitting blood pressure measurements have been taken. Blood pressure will be measured 3 times: 1 time after the patient

has been in a supine position for 5 minutes, 1 time after the patient has been standing for 1 minute, and 1 time after the patient has been standing for 3 minutes. A decrease in systolic blood pressure of  $\geq 20$  mmHg or diastolic blood pressure of  $\geq 10$  mmHg in either of the standing measurements or the presence of lightheadedness or dizziness during the test is considered abnormal and may justify a change in study medication dose at the Investigator's discretion.

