### 15.3. Appendix C: Protocol History

Protocol Version	Date Issued	Rationale for Update
Amendment 6 – Global	15 November 2022	
 
• Added Sparsentan + SGLT2 Inhibitor Sub-study to the protocol
 
• Global consolidation of protocol
 
• Updated information for COVID-19 Adverse Event/Serious Adverse Event reporting
 

Amendment 5-DE (country specific for Germany)	03 May 2021	
 
• Revised efficacy endpoints
 
• Specified single-tablet consumption based on availability during OLE period
 
• Included Interim Analysis
 
• Revised Schedules of Study Events
 
• Updated information for Physical Examination and specified measurement of heart rate for orthostatic hypotension detection
 
• Revised clinical laboratory assessments and removed serum pregnancy test for OLE period
 
• Specified condition when study medication cannot be resumed
 
• Added ECG measurements for all visits except visit 4 for DB period from screening through Week 36, for all visits for DB period from Week 48 through End of DB period, and for OLE period from Week 110 through Week 186, except for Week 116
 
• Added minor edits throughout
 

Amendment 5 – Global	06 April 2021	
 
• Revised efficacy endpoints
 
• Specified single-tablet consumption based on availability during open-label extension period
 
• Included Interim Analysis
 
• Revised Schedules of Study Events
 
• Updated information for Physical Examination and specified measurement of heart rate for orthostatic hypotension detection
 

Protocol Version	Date Issued	Rationale for Update
		
 
Revised clinical laboratory assessments and removed serum pregnancy test for open-label extension period
 
Specified condition when study medication cannot be resumed
 
Revised list of concomitant medications for both double-blind and open-label extension periods
 
Added minor edits throughout
 

Amendment 4-DE (country specific for Germany)	13 July 2020	
 
Added open-label extension period to protocol
 
Updated overall sample size and removed the sample size assessment
 
Added guidance for working with restrictions related to COVID-19
 

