### 5.4. Change from Planned Protocol Analyses

The analyses specified in this SAP are consistent with [PROTECT Protocol Amendment 5](#).

This SAP also clarifies which visits will contribute to the longitudinal analyses for efficacy if model convergence issues arise due to sparsity of data at later visits at the time of the primary analysis (Section 8.1).

The following analyses are included to address the recent Food and Drug Administration recommendations in the 27 May 2021 Advice letter (Reference ID: 4802510):

- Additional sensitivity analysis of the key secondary efficacy endpoint of the eGFR chronic slopes, defined as the slopes of eGFR following the initial acute effect of randomized treatment, at 1 year and 2 years via a mixed-effects model with linear spline with knot or change point at Week 6 with available eGFR data at primary analysis for 1 year and at the final analysis for 2 years as described in [Section 8.6.3.1](#).

- Additional sensitivity analyses for the primary and key secondary endpoints using data during the double-blind period including after premature treatment discontinuation (ie, a treatment policy approach) as described in [Section 8.5.2](#) and [Section 8.6.3](#).

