### **6.2. Data Conventions**

The precision of original measurements will be maintained in summaries, when possible.

For tables where rounding is required, rounding will be done at the final stage of the calculation to the nearest round-off unit. For example, when rounding to the nearest integer, values  $\geq XX.5$  will be rounded up to  $XX + 1$  (eg, 97.5 will round up to 98), while values  $< XX.5$  will be rounded down to  $XX$  (eg, 97.4 will round down to 97).

Percentages based on frequency counts will be based on available data, and denominators will generally exclude missing values, unless otherwise stated. For frequency counts of categorical variables, categories whose counts are zero will be displayed for completeness. For example, if

none of the patients discontinued due to “lost to follow-up,” this reason will be included in the table with a count of 0. Percentages based on frequency counts of case report form (CRF) collections (eg, demographic categories) will be presented as a whole number (no decimal places), and nonzero values less than 0.5% will be presented as “<1%.” Values less than 100% but that round up from 99.5% to 100% will be presented as “>99%.”

Quantitative laboratory tests containing less than (<) and greater than (>) symbols are test results that are below and above quantifiable limits, respectively. In order to retain these values for analysis purpose, values will be imputed as the numeric portion of the result.

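### SAP 10.5 counts orthostatic falls only above 20/10 mmHg, while Protocol 9.6 calls the test abnormal at 20/10 mmHg or more

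*SAP*

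**What the plan says.** Protocol Section 9.6 sets out the orthostatic test. Blood pressure is read once after the patient "has been in a supine position for 5 minutes, 1 time after the patient has been standing for 1 minute", and once more after 3 minutes of standing. A systolic fall of at least 20 mmHg or a diastolic fall of at least 10 mmHg "in either of the standing measurements or the presence of lightheadedness or dizziness during the test is considered abnormal".

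SAP Section 10.5 introduces its two rows with "For the analysis of orthostatic hypotension, the number and percentage of patients with". The systolic row is the "number and percentage of patients with >20 mmHg decrease in systolic blood pressure at any time". The diastolic row applies a cut-off of more than 10 to the "mmHg decrease in diastolic blood pressure at any time will be presented". Neither row says which reading the decrease is measured from.

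SAP Section 5.4 says of Protocol Amendment 5: "The analyses specified in this SAP are consistent with" it. That section lists no departure on orthostatic testing. No other part of the SAP applies the at-or-above rule.

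**The concern.** The SAP rows are labelled as the analysis of orthostatic hypotension, and the protocol already defines an abnormal orthostatic test by blood pressure. A reader of the study report would expect the two to match. They differ in the inequality for both systolic and diastolic pressure, so a patient exactly at the threshold is abnormal by the protocol and uncounted by the SAP.

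The protocol has this test done at every visit and allows an abnormal result to bear on dosing at the investigator's discretion. The summary of that test should therefore count the results the protocol calls abnormal. What is at stake is the accuracy of two safety counts. No efficacy result is involved.

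**Working it through.** The plan gives no figure to reproduce here, so the check compares the two rules and applies them at the boundary.

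**Inputs**

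- Protocol 9.6: abnormal if the systolic fall is ≥20 mmHg or the diastolic fall is ≥10 mmHg at either standing reading. Symptoms during the test also count.
- SAP 10.5: systolic row if the fall is >20 mmHg at any time; diastolic row if the fall is >10 mmHg at any time.
- Protocol 9.6: each positional value is a single reading. The sitting value, by contrast, is the mean of the last 2 of 3 readings.
- Recording step *s*: not given. SAP Section 6.2 says only "The precision of original measurements will be maintained in summaries, when possible". I assume *s* = 1, 2 or 5 mmHg.

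**Step 1. Boundary cases** (falls in mmHg, read as supine to standing, blood-pressure criteria only)

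| Systolic fall | Diastolic fall | Protocol abnormal | SAP systolic row | SAP diastolic row |
|---|---|---|---|---|
| 20 | 0 | yes | no | no |
| 0 | 10 | yes | no | no |
| 20 | 10 | yes | no | no |
| 20 | 15 | yes | no | yes |
| 21 | 0 | yes | yes | no |
| 0 | 11 | yes | no | yes |
| 19 | 9 | no | no | no |

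The first three cases are abnormal under the protocol and appear in neither SAP row. The fourth is missing from the systolic row only.

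**Step 2. Direction.** The SAP counts falls at any time, so a patient's largest fall decides the row. For systolic pressure:

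SAP row = N(largest fall ≥20) − N(largest fall = 20).

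The same holds for diastolic pressure at 10. Each row is therefore equal to or below the count on the matching protocol criterion, in both arms.

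**Step 3. Can exact ties occur?** Yes. A fall is the difference between two single recorded values, so on any of the assumed steps 20 and 10 are attainable values.

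**Step 4. Effective cut-off.** The first fall above 20 on a grid of step *s* is 20 + *s*, and the first above 10 is 10 + *s*:

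| *s* (assumed) | SAP systolic starts at | SAP diastolic starts at | Protocol starts at |
|---|---|---|---|
| 1 | 20 + 1 = 21 | 10 + 1 = 11 | 20 / 10 |
| 2 | 20 + 2 = 22 | 10 + 2 = 12 | 20 / 10 |
| 5 | 20 + 5 = 25 | 10 + 5 = 15 | 20 / 10 |

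The upward shift equals *s*: 1, 2 or 5 mmHg.

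**Step 5. Number of patients.** This would need the distribution of postural falls, which neither document gives, so I state no count.

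**Step 6. The other reading.** If the decrease were taken from baseline, the ordering in Step 2 would not apply. The rows would then not measure a postural fall at all, and the label would be wrong for a different reason.

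**The case against.** The strongest reply is that the two passages serve different purposes. Protocol 9.6 is a rule for the clinic. Orthostatic change is not a listed safety endpoint, and the protocol plans no orthostatic table. Protocol 12.8.1 leaves vital-sign reference ranges to the SAP. The other change rows in SAP 10.5 are also strict, so the SAP may be following its own convention.

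Part of this stands. No planned protocol analysis is contradicted, and the strict convention is real for changes from baseline. But Section 12.8.1 delegates low, normal and high ranges, not a test that Section 9.6 has already defined. The same list in SAP 10.5 uses inclusive cut-offs elsewhere (≤100 mmHg systolic, ≤60 mmHg diastolic), in line with the protocol's own limits.

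A second reply is that the point is conditional. The SAP names no reference reading, and the table shells mentioned in SAP 6.1, which are not supplied, may settle it. That is correct, and it is a further reason to amend the sentence.

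A third is that the protocol rule is a composite that includes symptoms, so aligned single rows would still not reproduce it in full. That is also true. It leaves the blood-pressure mismatch in place, because the shortfall in Step 2 is against the matching single criterion, not the composite.

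A fourth is version. The SAP was written to Amendment 5, whose text of Section 9.6 is not supplied. The protocol history describes an Amendment 5 change here: "Updated information for Physical Examination and specified measurement of heart rate for orthostatic hypotension detection". It mentions no change of threshold under Amendment 5 or Amendment 6, but it is a summary, so a version difference cannot be excluded.

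Finally, little information is lost. A patient at exactly 20 mmHg systolic still appears in the diastolic row if that fall exceeds 10, all readings go into patient listings, and hypotension adverse events are summarised separately under SAP 10.1.2. This limits the consequence but does not correct the rows.

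**Conclusion.** The concern holds and is minor. As written, SAP 10.5 does not use the blood-pressure thresholds by which Protocol 9.6 defines an abnormal orthostatic test, and the SAP does not acknowledge the difference. On the supine-to-standing reading, each row omits the patients whose largest fall is exactly at threshold, so it can only equal or fall below the protocol-based count, in both arms.

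The effective cut-off rises by 1, 2 or 5 mmHg, depending on an assumed recording step. The number of patients affected is unknown. No between-arm bias is shown, and no hypothesis test, alpha, power or sample size is touched. The conclusion rests on the supine-to-standing reading and on Section 9.6 having had the same thresholds under Amendment 5.

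**What to change.** In SAP 10.5, define the two rows as a fall of ≥20 mmHg systolic and ≥10 mmHg diastolic, measured from the supine reading to either the 1-minute or the 3-minute standing reading at the same visit. If the strict cut-offs are intended, say so and justify the difference from Protocol 9.6; the reference reading should be named in either case. A row for patients meeting either blood-pressure criterion is optional. The rows would still not cover the protocol's symptom criterion, so they should be described as blood-pressure criteria only.

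The cost is one sentence in the SAP and one table derivation from positional readings already recorded. No new data are needed, and the change concerns the analysis definition only, not any dosing rule at the sites.

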## **10.6. Physical Examination**

The number and percentage of patients with physical examination abnormalities at each visit will be summarized and presented by body system.

### **10.6.1. Peripheral Edema**

The presence and staging of peripheral edema will be summarized by frequency counts and percentages based on the following grades: 0, 1+ (trace), 2+ (mild), 3+ (moderate), and 4+ (severe), where 0 denotes no presence of edema. A shift table indicating changes in edema severity from baseline to worst (including scheduled and unscheduled), last value (scheduled and unscheduled), and at each scheduled post-baseline visit will be provided by treatment group.

